### 7.1.1 Inclusion Criteria

1. **All eligible participants:**
  - a. Are capable of providing informed consent or have a legal representative authorized to give consent on behalf of the participant, or in the case of underage (as defined by local regulations in each country) participants, are able to provide their informed assent together with consent from a parent or guardian; and
  - b. Are capable of complying with study procedures, including fasting, blood sampling and lumbar puncture; and
  - c. Are participating in the Enroll-HD study; and
  - d. Will have had an Enroll-HD visit within three months prior to the Annual Screening Visit.
2. For the **Healthy Control** group, participants eligible are persons who meet the following criteria:
  - a. Are 18-75 years of age, inclusive, at the time of consent; and
  - b. Have no known family history of HD; or
  - c. Have known family history of HD but have been tested for the huntingtin gene CAG expansion and are not at genetic risk for HD (CAG < 36).
3. For the **Early Pre-manifest HD** group, participants eligible are persons who meet the following criteria:
  - a. Are 18-75 years of age, inclusive, at the time of consent; and
  - b. Do not have clinical diagnostic motor features of HD, defined as Unified Huntington's Disease Rating Scale (UHDRS) Diagnostic Confidence Score < 4; and
  - c. Have CAG expansion  $\geq 40$ ; and
  - d. Have burden of pathology score, computed as  $(CAG - 35.5) \times \text{age}$ , < 250.
4. For the **Late Pre-manifest HD** group, participants eligible are persons who meet the following criteria:
  - a. Are 18-75 years of age, inclusive, at the time of consent; and
  - b. Do not have clinical diagnostic motor features of HD, defined as Unified Huntington's Disease Rating Scale (UHDRS) Diagnostic Confidence Score < 4; and
  - c. Have CAG expansion  $\geq 40$ ; and

- d. Have burden of pathology score, computed as  $(CAG - 35.5) \times \text{age} \geq 250$ .
5. For **Early Manifest HD** group, participants eligible are persons who meet the following criteria:
  - a. Are 21-75 years of age, inclusive, at the time of consent; and
  - b. Have clinical diagnostic motor features of HD, defined as UHDRS Diagnostic Confidence Score = 4; and
  - c. Have CAG expansion  $\geq 40$ ; and
  - d. Have Stage I or Stage II HD, defined as UHDRS Total Functional Capacity (TFC) scores between 7 and 13 inclusive.
6. For **Moderate Manifest HD** group, participants eligible are persons who meet the following criteria:
  - a. Are 21-75 years of age, inclusive, at the time of consent; and
  - b. Have clinical diagnostic motor features of HD, defined as UHDRS Diagnostic Confidence Score = 4; and
  - c. Have CAG expansion  $\geq 40$ ; and
  - d. Have Stage III HD, defined as UHDRS TFC scores between 3 and 6, inclusive.
7. For **Advanced Manifest HD** group, participants eligible are persons who meet the following criteria:
  - a. Are 21-75 years of age, inclusive, at the time of consent; and
  - b. Have clinical diagnostic motor features of HD, defined as UHDRS Diagnostic Confidence Score = 4; and
  - c. Have CAG expansion  $\geq 40$ ; and
  - d. Have Stage IV HD, defined as UHDRS TFC scores between 0 and 2, inclusive.
8. For **Juvenile Manifest HD** group, participants eligible are persons who meet the following criteria:
  - a. Are  $\geq 11$  years of age at the time of consent; and
  - b. Have clinical diagnostic features of juvenile HD, defined as UHDRS Diagnostic Confidence Score = 4 aged  $\leq 20$  years; and
  - c. Have CAG expansion  $\geq 40$
9. For **Incomplete Penetrance HD** group, participants eligible are persons who meet the following criteria:
  - a. Are 18-75 years of age, inclusive, at the time of consent; and
  - b. Have CAG expansion of 36-39

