## 6. Study Design

### 6.1 Overall Study Design

This is a Phase 0 observational study.

**Recruitment:** Participants will be recruited at multiple sites in the UK, Europe, North America, South America and Australasia from among participants in the Enroll-HD study who will have had an Enroll-HD study visit within three months prior to the Annual Screening Visit.

**Study Visits:** Participants will attend two annual study visits: an Annual **Screening Visit** followed by an Annual **Sampling Visit**. During the Annual **Screening Visit**, which may coincide with an Enroll-HD visit, medical history, clinical and phenotypic data (including a screening blood sample) will be obtained. These data will determine participant eligibility for participation in the study and will be used in the analysis of biomarker data. Participants meeting the eligibility requirements of the study and willing to continue in the study, will return for an Annual **Sampling Visit** within 30 days of the Annual Screening Visit. During that visit, biosamples will be collected following a fast of at least 6 hours, or overnight: blood will be obtained via venepuncture and CSF will be obtained via lumbar puncture. Participants will be contacted by telephone approximately 24-72 hours after the Annual Sampling Visit. Some participants may be invited to return for an **Optional Repeat Sampling Visit** 4-8 weeks following the **Annual Sampling Visit** during their first year of enrolment.

Participants will attend annual visits at regular intervals after the first Annual Screening Visit (i.e. at 1, 2, 3 years and so on)  $\pm$  2 months. Participants will be encouraged to complete all annual visits; however, they are under no obligation to take part and will be able to skip an annual visit without being discontinued from the study. Participants who do not come for an Annual Sampling Visit for three consecutive years will be discontinued from the study, but they may enroll again at a later date, if they so consent. Participants who have already completed HDClarity Sampling Visits under earlier versions of this protocol may also participate in the longitudinal study if they meet the eligibility criteria. Enroll-HD visits will provide the clinical data for this study.

**Biosample Preparation:** Samples will be processed and stored as described in Sections 10.1, 10.2 and 10.3 until ready for analysis.

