**HDCLARITY SCHEDULE OF EVENTS**

Visit Type	Year 0 			Years 1, 2, 3 	
	Annual Screening	Annual Sampling	Optional Repeat Sampling	Annual Screening	Annual Sampling
Visit Window	-30 to -1 days	Day 0	Day 28 - 56	Annually $\pm$ 2 months	Within 30 days of Annual Screening Visit
Study Procedure					
Informed Consent / Assent	X				
Confirm Continued Consent / Assent		X	X	X	X
Inclusion/Exclusion Criteria review	X	X	X	X	X
Demographics update	X			X	
Confirm Enroll-HD core assessments completed within last three months	X			X	
Brief Physical Exam	X	X	X	X	X
Medical History update	X	X	X	X	X
Prior/Concomitant Medication update	X	X	X	X	X
Full Neurological Examination	X			X	
Focused Neurological Examination		X	X		X
Total Motor Score (TMS)		X	X		X
Vital Signs (BP, pulse, body temp)		X	X		X
Safety Laboratory Assessments	X			X	
Urine Pregnancy Test 	X	X	X	X	X
Adverse Events (AE)		X	X		X
Final Eligibility Check		X	X		X
Lumbar CSF Collection		X	X		X
Venous Blood Draw 		X	X		X
CSF and Blood Sample Processing		X	X		X
CSF QC Processing		X	X		X
Telephone Follow-Up within 1-3 days (concomitant medication and AEs)		X	X		X

 This sequence of visits will continue such that Informed Consent/Assent will be sought again every fourth year

 Urine pregnancy test to be performed for females of child bearing potential unless the participant is post-menopausal or not sexually active

 Obtain venous blood sample immediately after CSF collection is complete

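### Read as written, the age-21-at-consent limit leaves pre-manifest participants who consent at 18-20 and convert at 21 or later in the same consent period with no cohort, for one to three annual samplings

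*Protocol*

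**What the plan says.** Section 7.1.1 (repeated in the synopsis) sets these rules:

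- Early and Late Pre-manifest (3a, 4a): "Are 18-75 years of age, inclusive, at the time of consent". Criteria 3b and 4b add "Do not have clinical diagnostic motor features of HD, defined as Unified Huntington's Disease Rating Scale (UHDRS) Diagnostic Confidence Score < 4", and CAG must be at least 40.
- Early, Moderate and Advanced Manifest (5a, 6a, 7a): "Are 21-75 years of age, inclusive, at the time of consent". These cohorts also need a Diagnostic Confidence Score of 4 and CAG of at least 40, and are separated by TFC.
- Juvenile Manifest (8b): "Have clinical diagnostic features of juvenile HD, defined as UHDRS Diagnostic Confidence Score = 4 aged" 20 years or younger.
- Incomplete Penetrance (9b): "Have CAG expansion of 36-39".

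On timing, the Schedule of Events marks "Inclusion/Exclusion Criteria review" at every screening and sampling visit, in Year 0 and in Years 1-3. Its first footnote says: "This sequence of visits will continue such that Informed Consent/Assent will be sought again every fourth year". Obtaining consent and confirming continued consent are separate rows, and Section 8.1.1 places the former at the first Annual Screening Visit only. Section 8.1.1 also makes the sampling date conditional on meeting all eligibility requirements.

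No text says how an enrolled participant changes cohort, fixes the cohort at entry, or exempts enrolled participants from the age limit.

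**The concern.** The pre-manifest and adult manifest cohorts have different lower age limits (18 and 21), and both limits refer to age when consent was given. In a single enrolment that is harmless. In a longitudinal study, a participant's score can change between annual visits while age at consent stays the same until renewal. A young participant can then leave the pre-manifest definition without being able to enter a manifest one.

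The likely origin is the 2021 amendment. According to the change log, it introduced the open-ended longitudinal design with four-yearly re-consent and also lowered the minimum age for controls and pre-manifest participants from 21 to 18.

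At stake are the samples taken just after conversion in the youngest converters. Sections 4.1 and 15.1 name disease progression as one use of the longitudinal samples. Under the literal rule these samples would be missing because the participant progressed. If sites read the rule differently, whether the samples exist would depend on the site.

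**Working it through.** The protocol gives no figure to reproduce, so the check applies the rules in order.

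**Worked case.** CAG is 40 or more, consent is given at age 20 with a score below 4, and a score of 4 is first recorded at the Year 1 cycle, at age 20 + 1 = 21.

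1. Early and Late Pre-manifest: fails 3b and 4b, because the score is now 4.
2. Early, Moderate and Advanced Manifest: fails 5a, 6a and 7a, because age at consent was 20. TFC does not matter.
3. Juvenile Manifest: fails 8b, whether the age there means age when first rated 4 or current age, since both are 21.
4. Incomplete Penetrance: fails 9b, because CAG is not 36-39.

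No cohort remains. A new recruit consenting at 21 with the same CAG and score passes 5a-5c, 6a-6c and 7a-7c and is placed by TFC.

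**Which pre-manifest cohort.** It makes no difference. Late Pre-manifest at age 20 needs (CAG - 35.5) × 20 ≥ 250, so CAG ≥ 35.5 + 12.5 = 48. With CAG 45 the score is 9.5 × 20 = 190, which is Early Pre-manifest. Both cohorts end at 3b or 4b in the same way.

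**Length of the gap.** Consent covers Years 0-3 (Section 4.2.1), with new consent at Year 4. Age at conversion = age at consent + year first rated 4. Samplings missed = years from conversion to Year 3 inclusive, when age at conversion is 21 or over.

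| Age at consent | First rated 4 at Year 1 | Year 2 | Year 3 |
|---|---|---|---|
| 18 | age 19: Juvenile, none missed | age 20: Juvenile, none missed | age 21: Year 3 missed (1) |
| 19 | age 20: Juvenile, none missed | age 21: Years 2-3 missed (2) | age 22: Year 3 missed (1) |
| 20 | age 21: Years 1-3 missed (3) | age 22: Years 2-3 missed (2) | age 23: Year 3 missed (1) |

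At the Year 4 re-consent these participants are 22, 23 or 24, so 5a, 6a and 7a are met and the gap closes. Conversion first seen at or after that re-consent leaves no gap.

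The table uses completed years and visits on the anniversary; the ±2-month window can shift a case near a birthday. It reads 8b as age when first rated 4.

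**After the change.** With the lower limit tested at the current Annual Screening Visit, every participant in a gap cell is 21 or over and is placed by TFC. Missed samplings fall to 0. One overlap needs settling: someone first rated 4 at 20 meets 8b and, once 21, would also meet an adult manifest cohort. The current text already has this overlap after the Year 4 re-consent.

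**The case against.** The best reply is that these are entry criteria. Section 7 presents the cohorts as recruitment strata, and a limit tied to the date of consent is how an entry rule is written. No sentence says that sampling stops when a participant leaves a cohort definition. On that reading the converter continues to be sampled. The outdated label does limited harm, because each annual cycle has Enroll-HD assessments from the preceding three months and a Total Motor Score, and Section 5 says samples will be selected using the donor's clinical data.

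This stands as a possible reading, so it cannot be asserted that sampling will stop at every site. It does not remove the point: the protocol nowhere adopts that reading, and the visit-by-visit review and Section 8.1.1's condition on booking support the literal one.

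Three stronger conclusions are tempting and not supported:

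- **Discontinuation.** A reader might infer that three missed samplings end participation, since Section 6.1 says: "Participants who do not come for an Annual Sampling Visit for three consecutive years will be discontinued from the study". That wording concerns people who do not come; applying it to someone who attends screening and is turned away is an inference. Section 16.4 refers to not attending screening and sampling. Fresh consent is due at Year 4 anyway, and re-enrolment is allowed.
- **A large loss.** A reader might note that 6 of the 9 table cells show a gap. The cells are hypothetical combinations, not participants, and say nothing about how often conversion happens in them.
- **Loss of samples on both sides of conversion, or a biased estimate.** Samples taken before conversion are kept. The protocol fixes no progression analysis, so no defined estimate can be called biased.

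**Conclusion.** The point holds in a limited form. On the protocol's wording, a pre-manifest participant with CAG of 40 or more who consents at 18-20 and is first rated Diagnostic Confidence Score 4 at 21 or later within that consent period meets no cohort. The participant would miss one to three annual samplings until re-consent, while a new recruit of the same age and score would be accepted. This is a stated rule that conflicts with the longitudinal design, not merely an omitted detail.

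The conclusion assumes that consent means the Year 0 consent and that the criteria apply to enrolled participants at each visit. The first follows from the schedule's separate rows; the second is the natural reading of the schedule and Section 8.1.1, though an entry-only reading cannot be excluded. The documents give no count of entrants aged 18-20 or of their conversions. The number is probably small, which limits the priority but does not remove the inconsistency.

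**What to change.** In criteria 5a, 6a and 7a, in both the synopsis and Section 7.1.1, apply the lower age limit at the current Annual Screening Visit for participants already enrolled. Then add a short transition rule:

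- An enrolled pre-manifest participant who reaches Diagnostic Confidence Score 4 is reassigned to the matching manifest cohort by TFC and stays eligible for sampling, subject to the other criteria.
- A participant who meets 8b (score of 4 at age 20 or younger) stays in the Juvenile cohort, so that the Juvenile and adult manifest cohorts do not overlap.

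The cost is one phrase in three criteria, in two places, and the short rule, all of which can go into the next amendment. No visit or procedure is added, and no combination of age and score is admitted that a new recruit could not already enter with.

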## **5. Study Objectives**

The overall objective of this study is to generate a high quality CSF sample collection that can be used to identify and validate biomarkers for HD clinical development.

CSF and blood samples will be collected from select sites throughout the world using a standardized protocol. Careful collection of clinical and phenotypic data on each donor will enable us to appropriately select subsets of samples for each set of experimental assays.

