## 7. Study Population

Eight participant cohorts will be included in the study and recruitment will be balanced across cohorts as far as possible. However, recruitment to the moderate and advanced manifest HD cohorts is expected to be approximately 50% of recruitment to other cohorts

and recruitment to the juvenile manifest and incomplete penetrance HD cohorts will be independent of recruitment to other cohorts:

1. Healthy controls
2. Early Pre-manifest HD
3. Late Pre-manifest HD
4. Early Manifest HD
5. Moderate Manifest HD
6. Advanced Manifest HD
7. Juvenile Manifest HD
8. Incomplete Penetrance HD

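### Does the undated age limit of 20 in the Juvenile Manifest criterion leave cohort assignment unsettled?

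*Protocol*

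**What the plan says.** Section 7.1.1 of the protocol, repeated in the synopsis, defines the cohorts by age, Diagnostic Confidence Score, CAG length and, for manifest disease, Total Functional Capacity (TFC).

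- **Juvenile Manifest (criterion 8).** 8a sets a floor of 11 years at consent and no ceiling. 8b reads "Have clinical diagnostic features of juvenile HD, defined as UHDRS Diagnostic Confidence Score = 4 aged" 20 years or less, with no event or date attached to that age. 8c requires a CAG of at least 40. There is no TFC condition.
- **Early, Moderate and Advanced Manifest (criteria 5 to 7).** Each carries "Are 21-75 years of age, inclusive, at the time of consent", a score of 4 and a CAG of at least 40. They differ only in TFC. Early participants "Have Stage I or Stage II HD, defined as UHDRS Total Functional Capacity (TFC) scores between 7 and 13 inclusive"; Moderate takes 3 to 6 and Advanced 0 to 2. None has a condition on age at onset.

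Section 7 says that "recruitment to the juvenile manifest and incomplete penetrance HD cohorts will be independent of recruitment to other cohorts". This concerns recruitment and does not assign a person who fits two definitions. The Schedule of Events in section 8.1 marks "Inclusion/Exclusion Criteria review" at every screening and sampling visit, and its first footnote says "This sequence of visits will continue such that Informed Consent/Assent will be sought again every fourth year".

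**The concern.** The other age limits in section 7.1.1 are tied to consent. The one in 8b is not, and juvenile HD is defined nowhere else in the protocol. Two readings are possible, and each appears to leave something open.

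- **Age at onset.** A 30-year-old whose score reached 4 at 19 is Juvenile Manifest under criterion 8 and also belongs to one adult manifest cohort, with no stated precedence. Two sites could label the same kind of donor differently.
- **Current age.** Nobody is in two cohorts at consent. But someone who enters at 20 soon passes the limit, while the adult floor of 21 applies at consent, which is renewed only every fourth year. The protocol does not say whether the label stays or moves.

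At stake is whether a person counts in the balanced cohorts or in the separately recruited juvenile one, and whether juvenile-onset donors sit unmarked among adult-onset donors when samples are drawn by cohort.

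**Working it through.** The plan gives no figure to reproduce. The check compares the definitions, taking a score of 4 as persisting once reached.

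**1. Current-age reading.** Juvenile covers ages 11 to 20 and the adult manifest cohorts cover 21 to 75. The ranges do not meet, so no one is in two cohorts at consent.

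**2. Onset reading.** Take whole-year ages 21 to 75 (75 − 21 + 1 = 55) and TFC 0 to 13 (14 values), with a score of 4 reached by age 20 and CAG at least 40:

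| Second cohort | TFC values | Profiles |
|---|---|---|
| Early | 7 to 13 (7) | 55 × 7 = 385 |
| Moderate | 3 to 6 (4) | 55 × 4 = 220 |
| Advanced | 0 to 2 (3) | 55 × 3 = 165 |
| Total | 14 | 55 × 14 = 770 |

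All 770 profiles fall in exactly two cohorts. That confirms the overlap but does not measure it. The grid holds only profiles that already meet criterion 8, and the three TFC bands cover the whole scale without gaps, so the result is 100% by construction. It says nothing about how many such people exist.

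**3. Who becomes eligible.** At ages 11 to 20, a person with a score of 4 now must have reached it by 20, so both readings admit the same people. At ages 21 to 75, anyone meeting criterion 8 under the onset reading already meets one of criteria 5 to 7. Across 11 to 75 the choice of reading therefore changes no one's eligibility under the cohort definitions, only the label. The readings admit different people only above 75, where the onset reading alone would let someone in.

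**4. Which reading the text favours.** Criterion 8a already governs current age. Had 8b meant current age, 8a would naturally have run from 11 to 20; instead it is the only cohort age rule with no ceiling. In 8b the age sits beside the diagnostic score and qualifies it. The adult floor of 21 is compatible with a current-age limit, but it does not outweigh these two points. Section 7.1 also lists people diagnosed with juvenile HD separately from those with early, moderate or advanced HD. That is not a precedence rule, but it points to the cohort named for the condition.

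**5. What the label controls.**
- Balance across cohorts is sought only so far as it can be achieved (section 7), with no fixed quotas.
- Section 5 says that data on each donor will "enable us to appropriately select subsets of samples for each set of experimental assays", so selection is not confined to the cohort label.
- Section 6.1 requires an analysis plan for each set of laboratory analyses before samples are sent, and section 15.1 requires a specific power calculation for each future study.
- Section 16.6 reserves samples from the incomplete penetrance cohort for particular studies. It places no such restriction on juvenile samples, so the label does not close off their use.

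**6. Change of label over time.** This is not peculiar to 8b. A participant can move from pre-manifest to manifest, or from Early to Moderate, in this open-ended design, and the protocol gives no relabelling rule for those moves either. Rewording 8b would not settle that general question.

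**The case for a change.** The best case for a change is that neither reading gives a complete rule. If onset is meant, a precedence sentence is missing; if current age is meant, 8a lacks a ceiling and the move past 20 is not covered. Sites apply the cohort definitions, so a later analysis plan cannot make their labels or the recruitment counts consistent. The question may also arise in practice: the juvenile cohort was added in October 2021 to a study that enrolled its first participant in January 2017, and earlier participants may return, so someone first recorded in an adult cohort could meet criterion 8 at the next visit. The repair would cost only a clause and a sentence.

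Much of this stands. The age in 8b has no anchor, no precedence is written down, and site labels could differ. What does not follow is harm to anything the study will conclude. Misplaced labels would shift cohort counts that have no fixed target, and analysts can regroup donors from the clinical data. A fuller remedy could also create its own inconsistency. Fixing a juvenile label across visits while leaving banked samples under their old label would give one returning donor two labels, and requiring documented onset would make the label depend on which records survive.

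**Conclusion.** No change to the plan is called for. Criterion 8b leaves its time point unstated, and on the more natural reading it overlaps the three adult manifest cohorts. This is a gap in detail that sites can fill sensibly by using the cohort named for the condition, and that analysts can check against the clinical data when they select samples. Stating the time point would be harmless tidying if the criteria were reopened for another reason.

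In size, the choice of reading changes no one's eligibility under the cohort definitions from 11 to 75, affects no hypothesis or power calculation in this protocol, and bears only on a label and on approximate recruitment balance. The number of people concerned cannot be derived from the protocol.

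The conclusion rests on two assumptions. The first is that a score of 4 persists once reached. The second is that the clinical data held on donors are good enough to recognise early onset. Section 6.1 says these data come from Enroll-HD visits, but the protocol does not list the variables, so this cannot be confirmed here. If onset were not recorded, a reworded criterion would be as hard to apply to donors already enrolled as the present one.
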